1. LIST OF ABBREVIATIONS

AE	Adverse event
CI	Chief Investigator
CRA	Clinical Research Associate (Monitor)
CRF	Case Report Form
CRO	Contract Research Organisation
CT	Clinical Trials
CTRG	Clinical Trials and Research Governance
CTU	Clinical Trials Unit
FASD	Fetal Alcohol Spectrum Disorder
GCP	Good Clinical Practice
GP	General Practitioner
HRA	Health Research Authority
ICF	Informed Consent Form
ICH	International Conference on Harmonisation
NHS	National Health Service
PAE	Prenatal Alcohol Exposure
PI	Principal Investigator
PIS	Participant/ Patient Information Sheet
PPI(E)	Patient and Public Involvement (Engagement)
R&D	NHS Trust R&D Department
REC	Research Ethics Committee
RSI	Reference Safety Information
SABPT	Surrey and Borders Partnership NHS Foundation Trust
SAE	Serious Adverse Event
SDV	Source Data Verification
SOP	Standard Operating Procedure
TMF	Trial Master File
TMG	Trial Management Group
TSC	Trial Steering Committee

UoS	University of Salford
UoS	University of Surrey
QMUL	Queen Mary University of London

1 INTRODUCTION

1.1 Background and rationale

Good parenting is vital for healthy child development, whilst ineffective parenting can lead to long-term adverse consequences for the child. Parenting children with neurodevelopmental disorders and/or behaviour problems can be associated with less positive, less consistent, and more ineffective parenting behaviours. Fetal Alcohol Spectrum Disorder (FASD) is a pervasive disorder that is increasingly recognised in the UK. Parenting these children is challenging, even for parents who have previously demonstrated parenting competence. Despite courses being developed for special groups such as autism spectrum disorders and attention deficit hyperactivity disorder, no effective parenting programmes exist for FASD.

Parents need support because FASD has significant added complexity compared to other conditions (3). This research addresses the vacuum caused by a lack of effective interventions by offering a bespoke FASD parenting programme, SPECIFiC, that is suitable for families with a child with a diagnosis of FASD. It aims to reduce family stress, and improve children's behaviour, ultimately changing children's life trajectories to improve their long-term outcomes.

In partnership with families, using funding from the Medical Research Council, we created 'SPECIFiC', an FASD parenting programme for those who care for children with a recent FASD diagnosis. SPECIFiC is a seven-week programme, where groups of six families meet weekly using video conferencing, along with an experienced trainer/therapist and an FASD-experienced parent.

1.2 Objectives

- To estimate recruitment and retention rates using a margin of error approach
- To demonstrate a signal of efficacy sufficient to justify progression to a full/definitive trial
- To establish a minimum clinically important difference (MCID) on the chosen primary outcome (Parenting Stress Index, PSI)
- To evaluate data collection completeness and the utility of secondary outcome measures
- To explore whether there are differences in outcomes depending on factors such as the facilitators, time since diagnosis and age of child.
- To estimate resource implications and costs of delivering SPECIFiC (not part of this SAP)
- To explore participants' experiences of SPECIFiC or being on the waiting list, and views on the design of the future definitive study (not part of this SAP).

2 Study Methods

2.1 Trial design

A two-arm randomised feasibility study of SPECIFiC training course against waitlist controls. The control group will receive treatment as usual during the intervention period and will receive the parenting intervention after the intervention period (see appendix A of the protocol). Families will be randomised 1:1 into the intervention or control arm. The study will not affect any aspect of the participants' clinical care. The 7-week course will be delivered by trained facilitators, following the manual created in a prior study funded by the Medical Research Council (MRC). All materials and information are incorporated into this

SPECIFiC_SAP_V2.0 20th November 2024

manual. The intervention was set up to be delivered online to groups of 6 on a rolling basis. This will minimise wait times and allow for timely access to the intervention for the controls, who will be on a waitlist. All participants are to be eventually offered the intervention. The primary outcome measure for efficacy (Parenting Stress Index, PSI) will be used to compare the SPECIFIC arm against treatment as usual at 16 weeks. Following this, those on the control group will receive the intervention. See Appendix A (protocol) for the trial flowchart.

2.2 Randomisation

Following a protocol amendment on 22 November 2023 (V3), the randomisation protocol was simple 1:1 allocation of families (index child and parent(s)) to (a) intervention arm or (b) waiting list control arm, using the online randomisation service SealedEnvelope.com. Prior to the protocol amendment, randomisation was balanced across cohorts of twelve (six in the intervention group, six waiting list controls).

2.3 Sample size

The target sample size is 120 families, randomly allocated in a 1:1 ratio between trial arms. This will be sufficient to demonstrate the feasibility outcomes of recruitment, retention, and adherence with satisfactory precision, but also to generate proof-of-principle that the intervention is likely to prove effective to support a funding application for a definitive trial. Data from the pre-feasibility study supports an average reduction pre- post-intervention on the PSI parenting stress scale of 11.44 (SD 14.62), representing an effect size of ~ 0.8 on Cohen's scale. If a moderate to large effect size was replicated in comparison to a control group measured at similar time points, this would justify moving to a definitive trial. To determine a significant effect size of >0.5 on Cohen's scale (~ 7.3 points on the PSI parent scale) comparing intervention with standard of care, with 80% power and at a one-sided significance level of 0.05, would require 102 families to be evaluated. To allow for an

attrition rate of 10% (withdrawal/loss to follow-up) we will seek to recruit >114 families. In our small-scale test-run of 9 families, retention was 100% and attendance was 97%, with 8 families attending all sessions and one family missing 2 sessions due to work commitments.

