3.1 Confidence intervals and P values

All applicable statistical hypothesis tests will be 2-sided and will be performed using a 5% significance level, unless otherwise specified. All confidence intervals presented will be 95% and two-sided.

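### Section 2.3 claims 80% power from a one-sided 5% test, but the SAP analyses PSI-4-SF two-sided; on the same unadjusted basis, power at 102 families is about 71%

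*SAP*

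**What the plan says.** Section 2.3 gives a recruitment target of 120 families, allocated 1:1. It takes an effect of 0.5 on Cohen's scale, about 7.3 PSI points, and states that detecting it "with 80% power and at a one-sided significance level of 0.05, would require 102 families to be evaluated". It then allows 10% attrition, giving a recruitment figure of 114.

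Section 3.1 sets the level for the analysis: "All applicable statistical hypothesis tests will be 2-sided and will be performed using a 5% significance level, unless otherwise specified". On intervals it allows no exception: "All confidence intervals presented will be 95% and two-sided".

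Section 5.3.1 reports the PSI-4-SF difference at 16 weeks with its 95% confidence interval, from a model adjusted for baseline, site and cohort. It mentions neither a one-sided test nor a 90% interval. Dummy Table 2b in section 6.1 has a p-value column for this outcome.

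On delivery, section 2.1 says: "The intervention was set up to be delivered online to groups of 6 on a rolling basis". Section 2.3 gives no intraclass correlation (ICC) and no correlation between baseline and follow-up.

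**The concern.** A sample size statement should describe the comparison that will be reported. Here the stated power belongs to a one-sided 5% test, which corresponds to a 90% two-sided interval, and the SAP never uses such an interval. Under section 3.1, the p-value and interval in Table 2b will be two-sided at the stricter level.

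Section 2.3 says the sample should also provide proof of principle to support a funding application for a definitive trial. A reader who takes the 80% as the chance of a significant result in Table 2b would expect more of this trial than section 2.3's assumptions deliver, and might read too much into a confidence interval that includes zero.

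**Working it through.** **Inputs.** From section 2.3: d = 0.5 (check: 7.3/14.62 = 0.499), 1:1 allocation, 80% power, one-sided 5%, 102 evaluable families (51 per arm), 10% attrition, target 120. From section 3.1: two-sided 5%. From section 2.1: groups of six. The ICC and the baseline correlation are not in the SAP, so any value used below is an assumption.

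**1. Reproducing the SAP's figure (one-sided 5%).** Normal approximation: n per arm = 2(z₁₋α + z₁₋β)²/d² = 2(1.645 + 0.842)²/0.25 = 49.5, so 50 per arm and 100 in total. The exact noncentral t calculation gives 50.15, so 51 per arm and **102** in total. Power by t is 79.9% at 50 per arm and 80.6% at 51. Attrition: 102/0.90 = 113.3, so 114. Both stated figures reproduce.

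**2. The same calculation, two-sided 5%.** Normal approximation: 2(1.960 + 0.842)²/0.25 = 62.8, so 63 per arm and 126 in total. The t calculation gives 63.77, so 64 per arm and **128** in total (79.5% at 63 per arm, 80.1% at 64). The 102 is therefore a one-sided figure.

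**3. Two-sided power at the SAP's sizes.** The noncentrality is d√(n/2).

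| Evaluable families | Per arm | d√(n/2) | Normal approximation | Noncentral t |
|---|---|---|---|---|
| 102 | 51 | 2.525 | Φ(2.525 − 1.960) = 71.4% | **70.6%** |
| 108 (120 × 0.90) | 54 | 2.598 | Φ(2.598 − 1.960) = 73.8% | **73.1%** |

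**4. What the unadjusted figure leaves out.** Two features of the plan work in opposite directions. These are normal approximations, two-sided, at 102 families.

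- Baseline adjustment multiplies the residual variance by (1 − r²). At an assumed r = 0.5 the noncentrality is 2.525/√0.75 = 2.916, and power is Φ(2.916 − 1.960) = 83% (about 82% by t).
- Groups of six in the intervention arm only multiply that arm's variance by 1 + 5 × ICC. At an assumed ICC of 0.05 the factor is 1.25. Without baseline adjustment, the standard error is √((1.25 + 1)/51) = 0.210 and power is Φ(0.5/0.210 − 1.960) = 66%. At an ICC of 0.10 it is 62%.
- Both together (r = 0.5, ICC 0.05): the standard error is √(0.75 × 2.25/51) = 0.182 and power is Φ(0.5/0.182 − 1.960) = 78%.
- Range over assumed r = 0.3 to 0.7: 75% to 94% with ICC 0, and 70% to 92% with ICC 0.05.

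The SD of 14.62 is quoted alongside a pre-post reduction, so it may be the SD of change. At r = 0.5 this makes no difference, because the variance of change is 2(1 − r) times the score variance, and 2(1 − 0.5) = 1.

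**The case against.** **The default in section 3.1 allows exceptions.** Section 2.3 does name a one-sided level. But it does so for the calculation only, section 5.3.1 specifies no one-sided test, and the sentence on confidence intervals has no exception. The mismatch stands.

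**The planned analysis may have more power than 71%.** This stands. Section 5.3.1 adjusts for baseline, and a moderate correlation could bring two-sided power at 102 back to around 80%. A reader might infer that the trial's own analysis has only 71% power, or less once group delivery is counted. The SAP does not support that: it gives neither the correlation nor the ICC, and counting only the one that lowers power would be selective. The simple design effect also differs from the SAP's model, in which cohort is a covariate and all controls share one code.

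**No decision depends on p<0.05.** This also stands. Section 2.4 says superiority is not sought. The proof-of-concept rule in section 5.3.1 asks whether the 95% interval fails to rule out 7.3 points, and the PSI-4-SF criterion in section 5.1.2 concerns which arm the estimate favours. With the SAP's SD and 51 per arm, the standard error is 14.62 × √(2/51) = 2.90. If the true benefit is 7.3 points, an interval of ±1.96 standard errors fails to exclude a 7.3-point benefit about 97.5% of the time. Reading 71% as the chance of passing either rule would therefore be wrong. Nor does any rule in the SAP turn a non-significant result into a finding of no effect.

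**Conclusion.** The point holds as an inconsistency between section 2.3 and sections 3.1 and 5.3.1. The sample size arithmetic is sound: 102 and 114 both follow from their inputs. What does not carry over to the two-sided analysis is the 80%. On section 2.3's own assumptions (d = 0.5, independent families, no covariates), two-sided power is about 71% at 102 evaluable families and 73% at 108, some 10 percentage points below the 80.6% and 82.6% that the one-sided level gives at those sizes. Reaching 80% would take 128 evaluable families.

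The sidedness result needs no outside assumption. Any figure for the adjusted model, or for group delivery, rests on a correlation and an ICC that the SAP does not supply. The consequences are limited because this is a feasibility trial whose progression rules are not significance tests, but the stated power should still match the stated analysis.

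**What to change.** Keep the two-sided 5% level and the 95% intervals in sections 3.1 and 5.3.1. In section 2.3, keep the one-sided calculation as the origin of 102, and add that under the two-sided level used in the analysis, power is about 71% at 102 evaluable families and 73% at 108. Label both figures as unadjusted and without allowance for delivery in groups.

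If an adjusted figure is added, state both assumptions behind it: the baseline to 16-week correlation, which raises power, and the intervention-arm ICC for groups of six, which lowers it. For example, a correlation of 0.5 gives about 83% with ICC 0 and 78% with ICC 0.05.

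Do not remove the mismatch by moving the PSI-4-SF comparison to a one-sided test or a 90% interval. Section 2.6 puts final data collection at 30 September 2024, and this SAP version is dated 20 November 2024, so that change would loosen the standard after the data were collected.

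The cost is a few lines of SAP text and a less favourable stated power. Recruitment and analysis do not change.

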2.4 Framework

As this is a feasibility trial, the focus is on the feasibility outcomes; we are not seeking to demonstrate superiority in this trial, although proof-of-concept will be investigated around the potential efficacy of the intervention in justifying a larger trial.

2.5 Statistical interim analyses and stopping guidance

No interim analyses were planned for this trial, and none have been undertaken.

2.6 Timing of final analysis

Final data collection was 30 September 2024. Data will be transferred to the study statistician at QMUL once preliminary checks have been completed and queries resolved by the trial team. Further data cleaning will be carried out by the statistician following receipt of the data and queries resolved with the trial team. The final analysis will start once all data queries have been resolved and the database has been locked.

2.7 Timing of outcome assessments

The timepoint for the proof-of-concept primary efficacy outcome assessment will be at 16 weeks, following the extended follow-up period. Note that the control group will have been receiving treatment as usual until the primary efficacy outcome assessment and the efficacy effect estimate will be the difference between intervention and no intervention. Data will

be collected from the control group 16 weeks after their intervention-baseline for future analyses but do not form part of this SAP.

Other questionnaire outcomes will also be assessed at 16 weeks. A secondary outcome is the comparison of the primary efficacy outcome at 8 weeks and 16 weeks, in the intervention group only. This outcome was added as part of a protocol amendment on 22 November 2023.

3 Statistical Principles

3.1 Confidence intervals and P values

All applicable statistical hypothesis tests will be 2-sided and will be performed using a 5% significance level, unless otherwise specified. All confidence intervals presented will be 95% and two-sided.

3.2 Adherence and protocol deviations

Adherence to the trial processes will be summarised by reporting key questionnaire completion rates by randomised group and timepoint. Adherence to the intervention will be summarised by reporting the number of sessions attended. Documented protocol deviations will be reported.

3.3 Analysis populations

The primary analysis will be conducted following the intention-to-treat (ITT) principle, in accordance with the randomised intervention. All randomised families with baseline data and at least one follow-up timepoint will be included in the primary analysis, regardless of adherence to the protocol. Participants that withdraw from completing further follow-up data

collection but do not withdraw consent for the use of their data collected so far, will be included in the intention-to-treat analysis. Per-protocol analysis for the candidate primary outcome (PSI-4-SF) will be performed to analyse the difference between arms only in those parents and children where the family was deemed to be protocol compliant, defined as attending five or more of the seven session. Per-protocol analyses will not be carried out for secondary outcomes, i.e. an ITT analysis will be performed for all secondary outcomes.

4 Trial Population

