5.3 Analysis methods

Statistical analysis will be mainly descriptive and focus on establishing the recruitment and retention rates that would indicate a trial is feasible, and to estimate parameters which will inform the sample size for the main trial. Recruitment, retention, and satisfaction rates will be presented by group with 95% exact confidence intervals.

Observed data from all randomised participants will be included in the analysis following the intention-to-treat principle.

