5.3.1 Primary outcome analysis

Primary analysis (ITT)

Candidate outcomes for the definitive trial including Parent stress (PSI-4-SF) will be compared between groups using a mixed model approach including all observed data at 16 weeks and adjusting for baseline measures and recruiting site. A binary variable will be included as fixed effect to indicate treatment allocation. Site, cohort, and baseline measure will be included as covariates; all control participants will be allocated a single cohort indicator. Inclusion of random subject effects will account for correlation between repeated outcomes on individual families. Estimated differences between groups and their 95% confidence intervals will be presented. The lower level of the 95% confidence interval for the difference between groups not ruling out an adjusted difference between groups of 7.3 points on the PSI-4-SF (as per the sample size calculation, section 3.4) will be considered sufficient to demonstrate proof-of-concept in the intervention. Subgroup analysis, such as whether outcomes differ according to time from diagnosis or age of index child will inform inclusion criteria and potential stratification factors for a larger trial. The PSI-4-SF outcome will also be available at 8 weeks in the intervention group only and will be reported; these data will not be included in the primary endpoint analysis. We will examine outcome profiles within the intervention group to see if any treatment effect is maximal during

training. These analyses are exploratory in nature and intended to help inform future research.

Per-protocol analysis

Sensitivity analyses will be conducted on the primary outcome to assess the robustness of results to failure to adhere to the protocol.

Per-protocol analysis for the candidate primary outcome (PSI-4-SF) will be performed to analyse the difference between arms in those parents and children where the family was deemed to be protocol compliant (see definition in Section 3.3). Per-protocol analyses will not be carried out for secondary outcomes.

Subgroup analyses

Subgroup analysis, such as whether outcomes differ according to time from diagnosis or by the age of the child will be done by adding the relevant factors to the mixed model as additional covariates and including an interaction term. The results from these analyses will inform inclusion criteria and potential stratification factors for a larger trial.

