5.4 Missing data

Missing data will be summarised. The reasons for systematic missingness will be explored.

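### The intention-to-treat primary set in SAP 3.3 excludes families with no baseline score even when their 16-week PSI-4-SF is observed, contrary to 5.3 and 5.3.1, and no rule covers a missing baseline

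*SAP*

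**What the plan says.** Three sections of the SAP describe who enters the primary analysis.

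- **3.3 Analysis populations** invokes the intention-to-treat principle and then says "All randomised families with baseline data and at least one follow-up timepoint will be included in the primary analysis".
- **5.3 Analysis methods** invokes the same principle with no baseline condition: "Observed data from all randomised participants will be included in the analysis following the intention-to-treat principle".
- **5.3.1 Primary outcome analysis** compares the arms "using a mixed model approach including all observed data at 16 weeks and adjusting for baseline measures and recruiting site".

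On missing values, **5.4** says only "Missing data will be summarised. The reasons for systematic missingness will be explored". No section says what happens to a family whose baseline score is absent.

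**The concern.** Baseline is only a covariate here. Dropping a randomised family with an observed primary outcome because a covariate is missing departs from the set that 5.3 promises, and the SAP does not call its set modified.

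The PSI-4-SF difference is one of the four progression criteria in 5.1.2, and 5.3.1 judges its confidence interval against 7.3 points. The CONSORT count of families analysed (4.1) also depends on which section is followed. Section 2.6 gives 30 September 2024 as final data collection, and this SAP version is dated 20 November 2024. The choice between two readings would therefore be made with the data already collected.

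**Working it through.** **1. The three sections applied to one family.** Take a randomised family with a 16-week PSI-4-SF and no baseline PSI-4-SF.

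- Under 3.3 it is out, because the baseline condition fails.
- Under 5.3 it is in, because its data are observed and it was randomised.
- Under 5.3.1 it is in by the words on 16-week data. In practice it is out, because the model needs a baseline value and 5.4 supplies none.

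Deleting the condition in 3.3 would therefore not be enough. A rule for the missing covariate is needed as well.

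**2. The plan's own figure.** Inputs from 2.3: standardised difference 0.5 ("To determine a significant effect size of >0.5 on Cohen's scale (~ 7.3 points on the PSI parent scale"), SD 14.62, one-sided 5%, power 80%.

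- Normal approximation: n per arm = 2(1.645 + 0.842)² / 0.5² = 49.5, so 50 per arm and 100 in total.
- Two-sample t-test: 50.15, so 51 per arm and 102 in total, as stated.
- Attrition: 102 / 0.9 = 113.3, so 114, as stated.

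**3. Power lost by exclusion.** The share f with a 16-week score but no baseline is not in the SAP. I assume 2% to 10%. With n = 51(1 − f) per arm, power = Φ(0.5·√(n/2) − 1.645), ignoring the gain from baseline adjustment.

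| f | families analysed | one-sided power |
|---|---|---|
| 0 | 102 | 81.1% |
| 2% | about 100 | 80.4% |
| 5% | about 97 | 79.3% |
| 10% | about 92 | 77.4% |

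**4. Precision gained by keeping the families.** Let ρ be the baseline-to-16-week correlation (assumed 0.6) and let missingness be unrelated to arm and outcome.

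- Excluding: variance is proportional to (1 − ρ²)/(1 − f).
- Keeping with the pooled mean baseline: variance is proportional to (1 − f)(1 − ρ²) + f.
- Ratio of the second to the first: (1 − f)[(1 − f) + f/(1 − ρ²)].

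With 1 − ρ² = 0.64:

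- f = 2%: 0.98 × (0.98 + 0.03125) = 0.9910, so the SE is 0.5% lower.
- f = 5%: 0.95 × (0.95 + 0.0781) = 0.9767, so 1.2% lower.
- f = 10%: 0.90 × (0.90 + 0.15625) = 0.9506, so 2.5% lower.

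Simulation puts the gain at about 0.2% to 3%. The ratio equals 1 when 1 − ρ² = (1 − f)/(2 − f), which is ρ of about 0.71 to 0.73 over this range of f. Above that, mean imputation costs a little precision: at ρ = 0.8 and f = 10% the ratio is 0.90 × (0.90 + 0.2778) = 1.06, so the SE is about 3% higher.

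**5. Bias.** Simulated baseline-adjusted linear model, SD 14.62, ρ = 0.6. The difference is intervention minus control, so a positive bias works against SPECIFiC.

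| Assumed missing baselines | Excluding | Pooled-mean baseline |
|---|---|---|
| Unrelated to arm, even if related to prognosis | within 0.03 of zero | within 0.03 of zero |
| Controls only, at random | within 0.04 of zero | within 0.03 of zero |
| About 10% of controls and 3% of intervention families, more often the more stressed | +0.46 | −0.19 |
| About 20% and 5%, same pattern | +0.91 | −0.43 |
| Worse-prognosis controls only; 2% / 5% / 10% of all families | +0.30 / +0.76 / +1.67 | −0.18 / −0.50 / −1.09 |

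Bias appears only when missingness depends on both arm and prognosis, and the two approaches then err in opposite directions.

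**The case against.** The best defence is that 3.3 only records what the model in 5.3.1 would do. A baseline-adjusted fit without imputation loses these families, and 5.3 is a general opening statement to a mainly descriptive analysis. The SAP shows no family with a 16-week score and no baseline, and losses would be visible through the completion rates in 3.2 and the flowchart in 4.1. The trial is also not seeking to show superiority (2.4). Much of this stands as to size, since the number affected may be zero. It does not remove the conflict: the sections define different sets under the same principle, and 5.4 leaves the missing covariate open.

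A reader might infer that exclusion biases the comparison, because families know whether they attend the course or wait and rate themselves. The documents do not support that step. Lack of blinding is a fair inference from the waitlist design, but the SAP does not say that baseline was collected after allocation was known. If it was collected before, exclusion costs precision only. The missing row under baseline in the Table 2b shell is a generic row. The figures 13, 20 and 33 in that table sit in an unlabelled block and cannot be read as missing baselines. Nor is there ground for discarding baselines dated after allocation, since nothing shows that any exist.

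**Conclusion.** The inconsistency holds on the text alone. Section 3.3 removes families that 5.3 and 5.3.1 include, and no rule keeps them in the adjusted model. The case for change rests on adherence to the stated intention-to-treat set and on not discarding observed primary outcomes.

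The numerical stake is small: at most about 4 points of power at an assumed 10% missing, and an SE gain of about 0.2% to 3% at an assumed correlation of 0.6. That gain disappears at a correlation of roughly 0.7. Bias is possible but not shown. In the less extreme assumed scenarios it would be about +0.5 to +0.9 points under exclusion and −0.2 to −0.4 under mean imputation, against a target of 7.3. Because the second favours SPECIFiC, imputation should not be presented as a cure for bias.

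**What to change.** - **3.3:** define the primary set as every randomised family with an observed 16-week PSI-4-SF, analysed as randomised. This also replaces the condition of at least one follow-up, which an 8-week score alone could meet although "these data will not be included in the primary endpoint analysis".
- **5.3.1 and 5.4:** where the baseline PSI-4-SF is missing, enter the mean baseline of all families, calculated without regard to arm, so that the family stays in the adjusted model.
- **Sensitivity analysis:** show the result restricted to families with an observed baseline. If the two results differ noticeably, say so, because they would err in opposite directions if missingness depended on arm and prognosis.
- **Table 1b:** report the number without a baseline score by arm.
- **5.3:** state the same set as 3.3 and 5.3.1.

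The cost is SAP wording, a line of code and one extra model fit on data already held. The drawback is weaker baseline adjustment for the few families affected.

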5.1.2 Pre-specified criteria for progression to a definitive RCT

The assessment for the next phase would consider progression criteria using a traffic light system if the Trial Steering Committee are satisfied that the following feasibility criteria are met (or can be reasonably mitigated with changes to the suggested protocol):

- *Recruitment: 0-25% = red; 26-50% = amber; 51-100% = green*
 - *Percentage of eligible parents invited who agree to participate.*
- *Retention: 0-50% = red; 50-70% = amber; 71-100% = green*

- *Percentage of those participating who complete the study.*
- *Satisfaction: 0-50%=red; 51-70%=amber; 71-100% =green*
 - *Percentage of those who express satisfaction with the session, as captured by the SPECIFiC session evaluation form.*
- *Estimated differences in primary outcome (PSI-4-SF total score) at 16 weeks: does not favour SPECIFiC=red; does not favour either SPECIFiC or TAU=amber; favours SPECIFiC = green.*

If red/amber results are obtained, the qualitative evaluation will be used to potentially remedy problems. Where it is deemed that identified problems cannot be managed, an RCT will not go ahead.

5.1.3 Secondary outcomes included in the SAP:

- MCID PSI-4-SF:
 - Estimate the difference in PSI-4-SF scores at 16 weeks with sufficient precision to inform a wider discussion around the clinical efficacy of the intervention and how the PSI-4-SF performs as a primary efficacy outcome for a future RCT.
- Data completeness:
 - Levels of missing data for the proof-of-concept primary efficacy outcome by timepoint
- Parent stress:
 - *(PSI-4-SF)* at Time 2 (8 weeks): to compare with the primary outcome (Time 3 PSI-4-SF) to determine whether intervention effects change over time. Note this outcome is only measured in the intervention group, due to the trial design (waitlist controls).
- Children's behavioural difficulties:
 - The Strengths and Difficulties Questionnaire (SDQ)
 - The Eyberg Child Behaviour Inventory (ECBI)

- Parents' psychological wellbeing:
 - *The Clinical Outcomes in Routine Evaluation–Outcome Measure (CORE-OM)*
- Parental mental health scale:
 - Depression Anxiety Stress Scales (DASS-21).
- Parenting self-efficacy:
 - Tool to measure Parenting Self-Efficacy (TOPSE)
- Group sizes

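### With no 8-week control scores, the 8-versus-16-week PSI-4-SF comparison cannot show whether the intervention effect changes or peaks; the primary set and random subject effect also need to match the 16-week-only model

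*SAP*

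**What the plan says.** **Time course.** SAP section 2.7: "A secondary outcome is the comparison of the primary efficacy outcome at 8 weeks and 16 weeks, in the intervention group only". Section 5.1.3 gives its purpose: "to compare with the primary outcome (Time 3 PSI-4-SF) to determine whether intervention effects change over time". The same entry acknowledges that the waitlist design leaves the control arm without an 8-week score. Section 5.3.1 adds an examination of profiles within the intervention group, to see whether any treatment effect peaks while the course is running, and labels it exploratory.

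**Primary set.** Section 3.3: "All randomised families with baseline data and at least one follow-up timepoint will be included in the primary analysis". It names neither the instrument nor the visit.

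**Primary model.** Section 5.3.1 says that the candidate outcomes, PSI-4-SF among them, "will be compared between groups using a mixed model approach including all observed data at 16 weeks", with baseline as a covariate. Of the 8-week scores it says "these data will not be included in the primary endpoint analysis". The same paragraph specifies a random term: "Inclusion of random subject effects will account for correlation between repeated outcomes on individual families".

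**The concern.** The main fault is in the time-course outcome. An intervention effect is a difference between arms. Whether it changes between weeks 8 and 16 depends on that difference at both times, and at week 8 there is no control value. A change in score within one arm also contains whatever would have happened without the course, including regression to the mean. The analysis could therefore report a growing or a stable effect when neither is true, and it is meant to inform the definitive trial.

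Two smaller faults concern agreement between sections. The rule in section 3.3 can be met at either of two visits in the intervention arm but at only one in the control arm, and the visit that makes the difference is then excluded from the model. The random subject effect is justified by repeated outcomes, but the model as specified keeps one PSI-4-SF time point per family. Whoever runs the analysis has to set one of these statements aside.

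**Working it through.** **Inputs from SAP section 2.3.** Target 120 families at 1:1, so about 60 per arm; effect 0.5 SD, about 7.3 points; SD 14.62; attrition 10%.

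**Assumptions (not in the SAP).** A fall of 4 or 5 points common to both arms between weeks 8 and 16; an effect waning from −10 to −5; correlation 0.6 between time points; 10% missing at 16 weeks, with 20% as a second value. Negative values mean lower stress.

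**1. The plan's own figure.** The normal approximation gives 2(1.645 + 0.842)²/0.5² = 49.5, so 50 per arm and 100 in all. The one-sided t calculation gives 51 per arm, 102 in all (power 0.806). Then 102/0.90 = 113.3, so 114. The stated 102 and 114 reproduce; this point does not touch them.

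**2. Time course.** Let C(t) be the mean control score at week t and E(t) the intervention effect, so that the intervention mean is C(t) + E(t). The within-arm change is

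D = [C(16) − C(8)] + [E(16) − E(8)].

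Only the second bracket is the change in effect. The first needs C(8), which is not measured, so D cannot be split. A simulation (200 runs per scenario, 60 per arm, SD 14.62, assumptions as above) agrees with the algebra:

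| True effect, week 8 → 16 | Common change | True change in effect | D by formula | D simulated |
|---|---|---|---|---|
| −7.3 → −7.3 | 0 | 0 | 0 | about 0.0 |
| −7.3 → −7.3 | −4 | 0 | −4 | −3.8 |
| −10 → −5 | 0 | +5 | +5 | +5.0 |
| −10 → −5 | −5 | +5 | 0 | −0.1 |

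In the second row a constant effect looks as if it grows. In the fourth, an effect that halves looks stable. D equals the change in effect only when the common change is zero, which the design cannot check.

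**3. Primary set.** With 60 per arm and 10% missing at 16 weeks, 60 × 0.90 = 54 families per arm have a 16-week score. Under the literal rule in section 3.3 the intervention arm has between 54 (no lost family gave a week-8 score) and 60 (all did), against 54 controls. At 20% missing it is 48 to 60, against 48. Adding the week-8-only families to the baseline-adjusted 16-week model changed the estimate by exactly 0.0 in every run, because they have no 16-week outcome.

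**4. Random subject effect.** With one outcome per family, Var(outcome given covariates) = subject variance + residual variance. The data inform only the sum, so the two parts cannot be estimated separately. The treatment coefficient is not biased by the redundant term.

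**The case against.** The case on the other side has force. The SAP discloses that week 8 is measured in one arm, calls the within-arm profiles exploratory, and says in section 2.4 that superiority is not sought. No progression criterion uses week 8. Planned reporting would show the true 16-week numbers: completion by group and time point (section 3.2), the CONSORT flow (section 4.1), and n, missing and withdrawn by arm (dummy Table 2b). Section 2.2 defines a family as the index child and one or more parents, so more than one score per family is conceivable, although the SAP does not say so.

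This limits how serious the point is but does not remove it. An exploratory label does not make the quantity estimable, and sections 2.7 and 5.1.3 list the comparison as a secondary outcome with a stated inferential purpose.

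A reader might infer three stronger things that the SAP does not support:

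- **That one-arm week-8 data decide or bias the primary result.** Section 5.3.1 excludes them, and under that rule the estimate does not move. Harm would arise only if they were pooled against the plan: in the simulation with a constant −7.3 effect and a 4-point common fall, pooling gave about −5.4, against about −7.4 from the 16-week model.
- **That the 10% in section 2.3 is loss between weeks 8 and 16.** It is overall attrition, so 6 extra families is the ceiling at that rate.
- **That week 8 necessarily falls after the seven-week course.** The SAP does not say when week 0 falls relative to the first session. The point does not need this, since the missing control value is enough.

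**Conclusion.** The time-course fault stands. The comparison of 8 and 16 weeks, and the within-arm profiles, cannot determine whether the intervention effect changes or when it is greatest. The error equals whatever change would have occurred without the course: 4 to 5 points under the assumed trends, which is more than half of the 7.3 points used for sample size. The actual trend is unknown, so the figures illustrate the error and do not predict it.

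The two mismatches also stand, as contradictions in wording. The primary-set rule can overstate the intervention arm's N by up to 6 families at 10% missing, or 12 at 20%, with no effect on the estimate under the stated model. The random subject effect is unidentifiable if each family gives one 16-week score. The between-arm comparison at 16 weeks is sound in these respects. The SAP should be corrected before analysis.

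**What to change.** 1. In sections 2.7, 5.1.3 and 5.3.1, state the 8-to-16-week outcome as a descriptive change in PSI-4-SF score within the intervention arm, with a 95% confidence interval. Delete the statements that it shows whether the intervention effect changes or peaks.
2. In section 3.3, define the primary set for PSI-4-SF as randomised families with a baseline and a 16-week score, by the same rule in both arms.
3. In section 5.3.1, remove the random subject effect from the PSI-4-SF model. If more than one score per family will enter at 16 weeks, say so, say whose scores they are, and keep the term on that ground. Keep the exclusion of 8-week data.

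The cost is a few lines of SAP text, with no new data and no change to the sample size. What is given up is a time-course conclusion that the data cannot support.
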